## 6.2 Efficacy

## 6.2.1 Part 1 (CHICO)

## 6.2.1.1 Primary efficacy variable and analysis

The primary efficacy variable will be sero-reduction (defined as  $a \ge 20\%$  reduction in optical density [OD]) or sero-conversion (defined as negative Immunoglobulin G [IgG] concentration) in the 60-day regimen group at 12 months post-treatment using two conventional ELISA serology tests. This sero-reduction (in subjects  $\ge 8$  months to < 18 years of age at randomization) or sero-conversion (in all subjects) is considered cure, and the primary variable is binary (cure, no cure). In the event of discordancy between the two conventional ELISA test results, the following will be considered:

• For sero-reduction, the average percentage of OD reductions for the two conventional ELISA tests will be used (e.g., Test #1 = 15% and Test #2 = 25%; average = 20% and, hence, cure).

BAY No. A2502/IMPACT No. 16027

Page:

- For sero-conversion, only when both test results are negative that the subject is considered as negative (i.e., cure).
- If one of the test results is missing, the subject is considered as "no cure".

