#### PROC FREQ;

TABLES group\*cured / RISKDIFFC;

WEIGHT counts;

RUN;

The analyses specified above (the proportion of subjects with sero-reduction or seroconversion and an asymptotic 95% CI for the 60-day nifurtimox regimen, and the difference of two independent proportions for the 60-day and 30-day regimens and an asymptotic 95% CI) will also be done using data from Days 7 (Visit 3), Days 30 (Visit 6), the EOT visit (Visit 8), and Days 240 (Visit 10). In the event of small sample sizes for the subgroups, an exact 95% CI will be calculated instead of an asymptotic one.

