## 6.2.1.2 Secondary efficacy variables and analysis

Secondary efficacy variables include clinical signs/symptoms of Chagas' disease (see Appendix 9.1), concentration test for *T. cruzi* (for subjects < 8 months of age ), non-conventional serologic testing, and disease state determined by qPCR ("cure" defined as Not Detectable / "no cure" defined as Detectable).

All secondary efficacy variables, except signs/symptoms of Chagas' disease, will be summarized overall and by treatment regimen at each assessment time for each age stratum.

Signs/Symptoms of Chagas' disease will be summarized for each item (see Appendix 9.1).

The relationship of conventional serology results to qPCR results will be done using frequencies of matches and mismatches on the determination of disease status, and phicorrelation and kappa coefficient to assess the degree of agreement. The relationship of nonconventional serology to conventional serology will be analyzed in the same way. The following SAS code will be used:

PROC FREQ;

TABLES group\*cured / CHISQ AGREE;

WEIGHT counts;

RUN;

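### SAP 6.2.1.2 contradicts itself: the text plans paired test agreement, but the SAS statement given for it names neither pair of test results

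*SAP*

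**What the plan says.** Assessing conventional serology against qPCR, and non-conventional against conventional serology, are exploratory objectives of Part 1 (protocol 4.1, SAP 2.1). The analysis is described in SAP 6.2.1.2, which matches protocol 10.3.2.1.

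- **Text.** "The relationship of conventional serology results to qPCR results will be done using" counts of matches and mismatches on disease status, with phi and the "kappa coefficient to assess the degree of agreement". For the second comparison, non-conventional "serology to conventional serology will be analyzed in the same way. The following SAS code will be used".
- **Code that follows.** A PROC FREQ step whose TABLES request is `group` by "cured / CHISQ AGREE", with a WEIGHT statement on `counts`. One such step is given for both comparisons.
- **Same request elsewhere.** In SAP 6.2.1.1, under the secondary analysis of the primary efficacy variable, the TABLES request is `group` by "cured / RISKDIFFC". The SAP describes that analysis as "the difference of two independent proportions for the 60-day and 30-day regimens and an asymptotic 95% CI".

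Both ratings needed for serology against qPCR exist as cure or no cure per subject. SAP 6.2.1.1 defines it for conventional serology, and SAP 6.2.1.2 defines it for qPCR (not detectable or detectable).

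**The concern.** Agreement between two tests is a property of pairs. Each subject contributes one result from each test, and the table crosses the two. The stated request has a single outcome variable, `cured`, and a second variable, `group`, that the SAP does not define. The only other use of that pair of names is the regimen comparison, so the likeliest explanation is that the earlier snippet was reused and only its options were changed.

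At stake is whether the phi and kappa say anything about the assays. A table of regimen by cure is 2x2, so the AGREE option would still return a kappa. That number would describe how cure differs between arms, not how often the tests match.

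**Working it through.** The plan states no phi or kappa, so there is no figure to reproduce. The check compares what the coded table and the paired table return for the same subjects.

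**Inputs**
- Arm sizes 200 and 100: about 300 subjects randomized 2:1 (SAP 3.1; protocol 10.4 gives 200 and 100).
- Cure rate 55%: the planning value for nifurtimox (protocol 10.4, SAP 6.5). Applying it to both arms is an assumption.
- Cure rate 40% in the 30-day arm: an assumption for the second illustration; it is not in the documents.

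**Formulas** for a 2x2 table [a, b; c, d] with total n:
- phi = (ad − bc) / √(product of the four margins)
- kappa = (po − pe) / (1 − pe), where po = (a + d)/n and pe = [(a + b)(a + c) + (c + d)(b + d)]/n²

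**1. Coded table, `group` read as regimen, 55% cure in both arms:** [110, 90; 55, 45].
- ad − bc = 4,950 − 4,950 = 0, so phi = 0.00.
- po = 155/300 = 0.5167.
- pe = (200 × 165 + 100 × 135)/90,000 = 46,500/90,000 = 0.5167.
- kappa = 0.00.

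Whenever the two arms have the same cure rate, ad = bc. The zero therefore does not depend on the 55% or on the 2:1 split.

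**2. Paired table, same 165 cured and 135 not cured, tests agreeing in every subject:** [165, 0; 0, 135].
- po = 1; pe = (165² + 135²)/90,000 = 45,450/90,000 = 0.505.
- kappa = 1.00 and phi = 1.00.

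**3. Paired table, tests independent, each 55% cured:** [90.75, 74.25; 74.25, 60.75].
- po = 151.5/300 = 0.505 = pe.
- kappa = 0.00 and phi = 0.00.

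The coded table is identical in cases 2 and 3, so it cannot tell perfect agreement from none.

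**4. Coded table with an assumed 55% versus 40% cure:** [110, 90; 40, 60].
- phi = (6,600 − 3,600)/√(200 × 100 × 150 × 150) = 3,000/21,213 = 0.141.
- po = 170/300 = 0.5667; pe = (200 × 150 + 100 × 150)/90,000 = 0.50.
- kappa = 0.0667/0.50 = 0.133.

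This reflects the arm difference alone. Its sign depends on the order of the levels: reversing the cure columns gives po = 130/300 = 0.4333 and kappa = −0.133.

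**5. `group` read as test type, one record per subject per test, tests agreeing in every subject:** [165, 135; 165, 135].
- po = 300/600 = 0.50; pe = (300 × 330 + 300 × 270)/360,000 = 0.50.
- kappa = 0.00 and phi = 0.00. The pairing is lost here too.

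**The case against.** The strongest reply is that the words govern. SAP 6.2.1.2, protocol 10.3.2.1 and the objectives all describe the intended comparison correctly. The snippet has no input data set and uses generic names with aggregated counts. A programmer following the text would build the paired table. Much of this stands: the defect is a mismatch between code and text, not a wrong choice of analysis.

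It is also fair that `group` is undefined, so reading it as regimen is an inference. If `group` held the comparator test's status and `cured` held serology cure, the code would return the right paired kappa. Nothing in the SAP supports that reading, and the only other use of the name is for regimen. The possibility does mean the code cannot be called wrong under every conceivable labelling.

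A reader might infer that both exploratory objectives rest on this one statement, or that a spurious finding of poor agreement would go into the report. The documents do not support either. The objectives rest on the prose definition. A table with 60-day and 30-day rows has no match or mismatch cells, so it could not supply the first output the text asks for, and the error would probably be noticed.

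The reply does not remove the contradiction. The SAP says this code will be used. For IHA against ELISA it sets out paired layouts (Tables 6–2 to 6–4); for these two comparisons SAP 6.2.1.2 gives no layout, and the code is the only operational detail.

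**Conclusion.** The point holds as an internal contradiction in SAP 6.2.1.2. The text calls for paired agreement, and the stated code identifies neither pair of results. If `group` is treatment regimen, the phi and kappa depend only on arm sizes and cure rates. At equal cure rates both are 0.00 whatever the true agreement, against a paired kappa of 1.00 when the tests agree in every subject. The size of any non-zero value rests on assumed cure rates, and its sign on level order, so only the zero at equal rates should be cited as a general result.

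The reach is limited to the two agreement analyses, which serve exploratory objectives although they sit under the secondary efficacy heading. It would be wrong to infer any effect on the primary endpoint or on the 60-day versus 30-day comparison, where crossing `group` with `cured` is the right table. This is a minor correction, worth making because a signed plan should not contradict itself on which table is built.

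**What to change.** Replace the single statement in SAP 6.2.1.2 with two TABLES requests, each crossing the two binary results per subject and each with CHISQ AGREE:

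- conventional serology cure by qPCR cure, for example `serology_cure*qpcr_cure`;
- conventional serology by non-conventional serology, for example `serology_cure*nonconv_cure`.

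The variable names are placeholders; the SAP should state how each result is coded. Running the tables by visit or by regimen is optional, since the text does not ask for it. The cost is a few lines of SAP code, with no new data and no change to the sample size. If programs have already been run with the statement as written, the agreement outputs need to be regenerated.

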## 6.2.1.3 Exploratory efficacy analysis and analysis

For the exploratory objective to assess the comparability of nifurtimox with benznidazole, the cure rate of 58% with a 95% CI (45%, 70%) from publication of de Andrade et al. in 1996 [2] will be referenced. If the lower limit of the same 95% CI for the primary efficacy variable (the 60-day nifurtimox regimen cure rate) is greater than 45%, nifurtimox will be deemed as comparable to benznidazole.

The comparison of conventional serology to IHA results will be done using a 3-by-3 table (Table 6-2) with the following categories:

- ELISA tests: sero-conversion and sero-positive (sub-categories: sero-reduction and others), where "others" refers to any sero-positive results that do not satisfy the definition of "sero-reduction".
- IHA test: negative and positive (sub-categories: titers decreasing and titers non-decreasing).

BAY No. A2502/IMPACT No. 16027

21 of 30

Page:

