⁵ Sero-conversion for the historical controls will be estimated from cure rates as presented in two publications.[15][16] See Section 5, Study Design, Justification of the design.

³ Text modified per Modification 2 (Amendment 1)

⁴ Exploratory objectives added as per amendment 2.

03 NOV 2020	Version 11.0	Page: 5 of 259
	 To assess the comparability of a 30-day re 60-day regimen of nifurtimox using quantir reaction (qPCR) at the 12-month follow-up To evaluate the relationship of convention reduction or sero-conversion) to qPCR usi and mismatches to assess agreement⁸ To evaluate the relationship of non-conver conventional serology⁹ Part 2 (CHICO SECURE) The primary objective of the LTFU part of the stude Assess the incidence of seronegative converty types of assay, recombinant ELISA, and ir assay (IHA), in subjects who were random one dose of the 60-day nifurtimox treatme external control group of untreated patient 	tative polymerase chain o (360 days from EOT) ⁷ al serology (as sero- ng frequencies of matches ntional serology to y is: ersion as confirmed by two ndirect hemagglutination nized and received at least nt regimen, compared to an
	the 4-year follow-up. The secondary objectives are:	
	 Assess the incidence of seronegative conversional states of assay (recombinant ELISA and II randomized and received at least one dose treatment regimen at the 4-year follow-up. Evaluate the proportion of responders who conversion as confirmed by two types of a and IHA) and no evidence of established of evaluated in electrocardiogram (ECG) recombined antigen ELISA, in subjects we received at least one dose of either the 60-treatment regimens compared to Visit 1 in the states of the series of the se	IA), in subjects who were of the 30-day nifurtimox show both seronegative ssay (recombinant ELISA ardiomyopathy as ordings. y recombinant ELISA and yho were randomized and or 30-day nifurtimox
	The exploratory objectives are:	
	 Assess the incidence of seronegative conversion of assay (recombinant ELISA and II categories (≤2 years, >2 years to ≤6 years, <18 years; age is defined as subject's age as a subject's age	IA) in subjects by age >6 to ≤ 12 years, >12 to
	• Assess the proportion of responders who s conversion and the incidence of seronegation by non-conventional serology in subjects we received at least one dose of either 60- or a regimens.	we conversion as confirmed who were randomized and

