• Assess the incidence of seronegative conversion as confirmed by two types of assay, recombinant ELISA, and indirect hemagglutination assay (IHA), in subjects who were randomized and received at least one dose of the 60-day nifurtimox treatment regimen, compared to an external control group of untreated patients with Chagas' disease at the 4-year follow-up.

³⁵ Text modified per Modification 2 (Amendment 1)

³⁶ Text added to include neurological examinations per Modification 10 (Amendment 1)

³⁷ Exploratory objectives added as per Amendment 2

³⁸ Sero-conversion for the historical controls will be estimated from cure rates as presented in two publications.[15][16] See Section 5, Study Design, Justification of the design.

³⁹ Text modified per Modification 2 (Amendment 1)

⁴⁰ Text modified per Modification 2 (Amendment 1)

⁴¹ Text modified per Modification 2 (Amendment 1)

⁴² Fourth objective added per Modification 2 (Amendment 1)

⁴³ IFA test added per Amendment 5.

⁴⁴ Replaced IFA with IHA per Amendment 6.

	Integrated Clinical Study Protocol BAY A2502 / 16027	
03 NOV 2020	Version 11.0	Page: 26 of 259

The secondary objectives are:

- Assess the incidence of seronegative conversion, as confirmed by two types of assay (recombinant ELISA and IHA), in subjects who were randomized and received at least one dose of the 30-day nifurtimox treatment regimen at the 4-year follow-up.
- Evaluate the proportion of responders who show both seronegative conversion as confirmed by two types of assay (recombinant ELISA and IHA) and no evidence of established cardiomyopathy as evaluated in electrocardiogram (ECG) recordings.
- Assess serial reduction in OD measured by recombinant ELISA and total purified antigen ELISA, in subjects who were randomized and received at least one dose of either the 60- or 30-day nifurtimox treatment regimen compared to Visit 1 in part 1 of the study.

The exploratory objectives are:

- Assess the incidence of seronegative conversion as confirmed by two types of assay (recombinant ELISA and IHA) in subjects by age categories (≤2 years, >2 years to ≤6 years, >6 to ≤12 years, >12 to <18 years; age is defined as subject's age at randomization).
- Assess the proportion of responders who show seronegative conversion and the incidence of seronegative conversion as confirmed by non-conventional serology in subjects who were randomized and received at least one dose of either 60- or 30-day nifurtimox treatment regimens.

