There are several choices for diagnosis of Chagas' disease and monitoring of drug efficacy after anti-parasitic treatment. Traditional parasitological methods, such as direct microscopic observation, xenodiagnoses, and hemoculture, show low sensitivities, limiting their usefulness. Microhematocrit is the method of choice to identify congenital infection because of its heightened sensitivity and the small amount of blood needed. Microscopic examination of cord blood or peripheral blood of the neonate by this technique is strongly recommended during the first month of life. For the monitoring of drug efficacy, the criterion of cure usually depends on serologic conversion of the anti-*T. cruzi* antibody response to negative. Sero-conversion in children and adolescents may occur several years after treatment, requiring long-term follow-up.

Sero-reduction (measured as a $\geq 20\%$ reduction of the ELISA absorbance [OD] value) at 12 months post-treatment will be considered equivalent to historical information on sero-conversion at subsequent time points after treatment.⁷²

Both primary and secondary study endpoints are based upon a target of $\geq 20\%$ decrease in antibody concentration (sero-reduction) to *T. cruzi* in conventional serological tests or negativization of serology. This is consistent with one previous study in children 6 to 12 years of age infected with *T. cruzi* in the intermediate (early chronic) phase of Chagas' disease [15]. Subjects were administered 5mg/kg benznidazole or placebo in a randomized fashion for 60 days, and followed for 48 months. At 12 months, a 21% reduction in concentration of Chagas' disease-specific antibodies compared to baseline (ELISA mean OD 0.467 [± 0.099] vs. 0.369 [± 0.107]) was observed in subjects who received benznidazole. For the subsequent time points of 18, 24, and 48 months, percent concentration reductions in antibody titer were reported as 23%, 29%, and 27%, respectively. After a 48-month follow-up, negative sero-conversion was detected in 11.3% (P<0.05) of the benznidazole group and only 4.5% of the placebo group.⁷³

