#### Primary analysis of the primary efficacy variable

The difference in the proportion of nifurtimox subjects with sero-reduction or sero-conversion (60-day regimen) and the proportion estimated from historical data will be tested using an asymptotic 2-sided 95% CI with a continuity correction of 1/2n for a single proportion.

The null hypothesis  $H_0$  is  $p_{nifurtimox} = p_{placebo}$ 

The alternative hypothesis H1 is  $p_{nifurtimox} \neq p_{placebo}$ , where pt is the cure rate for treatment t.

Superiority will be confirmed if the lower limit of the CI for the proportion of nifurtimox subjects (60-day regimen) with sero-reduction or sero-conversion is greater than 16%. The proportion and asymptotic 2-sided limits ( $p_l$ ,  $p_u$ ) of the 95% CI for  $p_{nifurtimox}$  can be computed by [3]

$$\hat{p}_{nifurtimox} = x/n$$

$$p_u = \hat{p}_{nifurtimos} + 1.96 \sqrt{\hat{p}_{nifurtimos}(1 - \hat{p}_{nifurtimos})/n} + 1/2n$$

$$p_l = \hat{p}_{nifurtimox} - 1.96 \sqrt{\hat{p}_{nifurtimox}(1 - \hat{p}_{nifurtimox})/n} - 1/2n$$

where x denotes the number of nifurtimox subjects with sero-reduction or sero-conversion and n the total number of subjects in 60-day regimen group. The SAS code will be:

PROC FREQ;

TABLES cured / BINOMIALC;

WEIGHT counts;

RUN;

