## Part 2 (CHICO SECURE)

According to Sosa-Estani [7, 7], the 48 months post treatment cure rate for benznidazole is about 5% as confirmed by two types of assay. For the primary objective, assuming a drop-out rate of 15%, the expected number of patients to be observed at the end of Part 2 (i.e. 48 months post treatment) in the 60-day regimen would be 170 out of the 200 patients in Part 1. Using the assumptions of 170 nifurtimox 60-day regimen patients in Part 2, a 5% cure rate, and that seronegative conversion events follow Poisson distribution, the estimated incidence rate is calculated to be 1.32% and the 95% CI of the incidence rate is (0.61%, 1.51%).

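### SAP 6.2.1.3 declares nifurtimox comparable to benznidazole on a 45% bar taken from one of the protocol's two sources, with no justified margin and no like-for-like reference

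*SAP*

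**What the plan says.** Protocol 4.1 and SAP 2.1 list, as an exploratory objective, the comparability of the 60-day regimen with historical benznidazole at 12 months. The protocol attaches a footnote to that objective (Synopsis, repeated in 4.1): "Sero-conversion for the historical controls will be estimated from cure rates as presented in two publications". It cites references 15 and 16.

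SAP 6.2.1.3 then takes one of these, reference 16, and refers to "the cure rate of 58% with a 95% CI (45%, 70%) from publication of" that trial. The rule begins "If the lower limit of the same 95% CI for the primary efficacy variable" and, for the 60-day cure rate, ends "is greater than 45%, nifurtimox will be deemed as comparable to benznidazole".

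The interval is the primary one, described in SAP 6.2.1.1 as an "asymptotic 2-sided 95% CI with a continuity correction of 1/2n for a single proportion".

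The benznidazole result of reference 15 is in the current protocol. Section 5.1 (Justification of the design) says that after 48 months "negative sero-conversion was detected in 11.3% (P<0.05) of the benznidazole group and only 4.5% of the placebo group".

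For placebo the SAP behaves differently: Table 6–1 sets out both publications.

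**The concern.** Three things looked wrong.

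- **Source.** The protocol names two publications for this comparison. The SAP uses one and gives no reason. SAP section 7, where changes to the planned analysis would be recorded, holds only version dates.
- **Criterion.** The bar is the lower confidence limit of the reference trial. That amounts to a margin of 58 − 45 = 13 percentage points, which neither document discusses.
- **Comparability of the two quantities.** Endpoint, time and age range differ between this trial and the reference, yet the rule returns a yes-or-no verdict.

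At stake is a statement in the study report about another drug that the comparison cannot carry. The objective is exploratory, so no primary or secondary conclusion depends on it.

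**Working it through.** **1. Reproduce the reference interval.** The current text gives 58% (45%, 70%) without counts. The Amendment 2 change log, in superseded wording, gives 37 of 64. I use that count only to check the interval. The exact (Clopper–Pearson) 95% interval for 37/64 = 57.8% is 44.8% to 70.1%, which rounds to the SAP's figures.

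**2. Find the pass mark.** The SAP's lower limit is p_l = p − 1.96·√(p(1−p)/n) − 1/(2n).

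With n = 200 (protocol 10.4):
- 104/200: 0.520 − 1.96·√(0.520·0.480/200) − 0.0025 = 0.520 − 0.0692 − 0.0025 = 0.448, fails.
- 105/200: 0.525 − 1.96·√(0.525·0.475/200) − 0.0025 = 0.525 − 0.0692 − 0.0025 = 0.453, passes.

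The observed rate must therefore reach 52.5%, which is 5.5 points below the reference estimate. SAP 6.5 still gives n = 260, where the pass mark is 134/260 (51.5%).

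**3. Probability that the rule passes** (exact binomial probability of reaching the pass mark):

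| True 60-day rate | n = 200 (105 or more) | n = 260 (134 or more) |
|---|---|---|
| 45% | 0.02 | 0.02 |
| 50% | 0.26 | 0.33 |
| 55% (planning value) | 0.78 | 0.88 |
| 58% | 0.95 | 0.98 |

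**4. Direction of the source choice.** The lower confidence limit of an 11.3% estimate must lie below 11.3%. The same rule applied to reference 15 would therefore set a bar below 11.3%, whatever that trial's denominator. The source in the SAP gives the harder test.

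**5. Set the two quantities side by side.**

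| | Tested | Reference behind the 45% |
|---|---|---|
| Endpoint | OD fall of 20% or more (from 8 months of age), or sero-conversion (all ages), on two conventional ELISAs | Published cure rate, which the protocol footnote uses to estimate sero-conversion |
| Time | 12 months after end of treatment | Trial with 3-year follow-up (protocol 5.1) |
| Age | Birth to under 18 years | 7–12 years (SAP Table 6–1) |

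Age matters on the protocol's own evidence. In the congenital series described in 5.1, conventional serology became negative after benznidazole at 6.6 months in children diagnosed before 8 months of age, and at 63.1 months in the older group.

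No like-for-like figure is available either. For the 12-month point, 5.1 gives only average antibody falls under benznidazole (21% in one trial, about 20% in the other), not the proportion of children with a fall of at least 20%.

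**The case against.** The strongest defence has four parts.

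- **The choice is conservative.** The SAP took the highest benznidazole rate in the documents, so adding the second source could only lower the bar. This stands. A reader might infer that the rule was tilted towards nifurtimox; step 4 shows the opposite.
- **The time and endpoint mismatch has a stated rationale.** Protocol 5.1 treats 12-month sero-reduction as equivalent to later sero-conversion in historical data, and the primary test rests on the same premise. This stands in part. It does not address age, and it cannot justify choosing one source: if 12-month sero-reduction stands for later sero-conversion, the 48-month 11.3% is as eligible as the 58%.
- **The SAP was entitled to fill in the detail.** Protocol 10.3.2.1 leaves exploratory analyses to the SAP, and the footnote sets no bar and no method of combining the sources. This is true, but it does not cover dropping a named source without comment.
- **The consequence is small, and sero-negative results are already shown separately** in SAP Table 6–2. That table compares ELISA with IHA; it does not put the 60-day sero-conversion rate beside the benznidazole results.

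Three stronger readings are tempting and are not supported:

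- **A benznidazole range reaching down to 5%.** The SAP does say that "the 48 months post treatment cure rate for benznidazole is about 5% as confirmed by two types of assay", but this is the stricter two-assay definition used for Part 2, from the same study and time point as the 11.3%. It does not belong beside a Part 1 ELISA benchmark.
- **A pooled bar from both sources.** The current text gives no benznidazole counts for either trial, so any pooled figure needs an assumed denominator.
- **The statement in 5.1 that direct comparisons cannot be made.** It concerns the two benznidazole trials against each other, and the same paragraph goes on to plan a comparison with benznidazole.

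**Conclusion.** The point holds as a protocol–SAP mismatch and an unsupported categorical conclusion. One of two named sources is used without explanation, the 13-point margin has no stated basis, and the reference differs from the tested quantity in endpoint, follow-up and age.

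Neither outcome of the rule is informative about benznidazole. A pass would rest on an unlike reference. A failure would be just as hard to read: at a true rate of 50% the rule fails with probability 1 − 0.26 = 0.74 at n = 200, although 50% is far above the 11.3% of the other source.

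The pass mark and probabilities assume the SAP's continuity-corrected interval and all 200 (or 260) subjects in the denominator. A reader might take the 58% to be a 3-year result. The current text gives the trial's follow-up length but does not date the 58%, so that is an inference; the argument needs only that the trial was followed for 3 years.

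The severity is low. The primary test against 16% and the 60-day versus 30-day comparison are untouched.

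**What to change.** In SAP 6.2.1.3, delete the 45% rule and the comparability verdict. Replace them with a descriptive table showing:

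- the 60-day rate for the 12-month composite, with its 95% CI;
- the 60-day rate for sero-conversion alone, with its 95% CI;
- the published benznidazole results from both references, 58% (45%, 70%) and 11.3%;
- for every row, the time point, assay, definition of response and age range.

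Add a sentence saying that no formal conclusion about comparability will be drawn.

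This changes SAP wording only. It needs no new data, and the exploratory objective is still served. The cost is that the sponsor gives up an exploratory claim.
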